### 13.2 Surgery

Patients who were not rendered NED will go to the survival follow-up (event monitoring) phase of the study where progression and survival information will be collected every 6 months for a maximum of 5 years post-registration. Subsequent treatment is at the discretion of the patient's medical team.

Patients who are rendered NED but refuse to begin the protocol-specific adjuvant treatment will go survival follow-up (event monitoring) phase of the study where progression and survival information will be collected every 3 months until disease progression and then every 6 months for a maximum of 5 years post-registration. Subsequent treatment is at the discretion of the patient's medical team

### 13.3 Adjuvant Treatment Phase

- 13.31 Patients who have not had disease recurrence and have not developed intolerable toxicity may continue treatment per protocol
- 13.32 Patients who have not had a disease recurrence but develop intolerable toxicity or are refusing further protocol treatment will go to observation phase of the study.
- 13.33 Patients who discontinue adjuvant treatment due to disease progression or other medical condition will go to the survival follow-up (event monitoring) period where disease and survival information will be collected every 3 months until disease progression and then every 6 months for a maximum of 5 years post registration.
- 13.34 Patients who have completed 8 cycles of adjuvant treatment will enter the observation phase of the study.

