## 4.2 Test Schedule for Arm C

Tests and procedures	Prior to Registration		Active Monitoring Phase						Observation 
				Neoadjuvant treatment	Surgical Period		Adjuvant Treatment		
	Pre-registration period	≤14 days prior to registration	After registration prior to start of treatment on C1D1	At completion of each Neoadj Treatment Cycle	After completion of ALL Neoadj Tx (prior to surgery)	At time of Surgery	≤7 days prior to start of Adjuvant Treatment	At completion of each Adjuvant Treatment Cycle	
Window				±3 days	±3 days			±3 days	±14 days
History and exam, Wt, PS	X			X			X	X	X
Height	X								
Adverse event assessment		X		X			X	X	X
Evaluation of kymphedema using NCI CTCAE v5.0 								X	X
Pregnancy test 		X							
Hematology group: CBC with differential		X		X			X	X	X
Chemistry group 		X		X			X	X	X
Neoadjuvant treatment period only: potassium, sodium		X		X					
INR 	X				X				
AM Cortisol					X				
TSH (reflex per institutional std)		X		X			X	X 	X
EBV testing		X 							
ECG 		X							
Clinical staging	X 								
Pathologic staging						X			

 Observation (clinical follow-up) every 3 months for max of 3 years post-surgery or until disease recurrence (only for patients who undergo surgery)

 At completion of adjuvant treatment and 12 months post surgery only; Please put results on Adverse Event: Other CRF

 For persons of childbearing potential only: Must be done ≤7 days prior to registration.

 AST, ALT, alkaline phosphatase, total & direct bilirubin, creatinine, random glucose

 Only for patients receiving therapeutic anticoagulation: stable anticoagulant regimen and stable INR

 Thyroid testing once per cycle or as clinically indicated

 EBV serology: Should include EBV VCA IgM. If IgM result is positive, patient is not eligible.

 Needed at baseline, thereafter as clinically indicated

 Submit clinical note or imaging documenting recurrent nodal metastasis, clinically detectable nodal metastasis, or metastatic involvement of more than one nodal basin

Tests and procedures	Prior to Registration		Active Monitoring Phase						Observation 
				Neoadjuvant treatment	Surgical Period		Adjuvant Treatment		

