## 8.2 Neoadjuvant Dose Modifications Based on Adverse Events

If all study medications are discontinued or all study medications are omitted for more than 28 days due to adverse events during the neoadjuvant period, the patient should proceed to surgery (once stable).

The days on which doses are omitted are not to be made up. For example, if vemurafenib is omitted on Days 1-3 of a cycle with recovery to Grade  $\leq 1$  on Day 4 of that cycle, the patient will receive vemurafenib on only Days 4-21 of the cycle.

If all study medications are discontinued due to adverse events during the adjuvant period, the patient should proceed to observation.

Providers may hold, delay, or reduce (in line with Section 8.1) doses, even in the absence of a requirement to do so in this table (Section 8.2) per clinical judgement to maximize patient safety. For example, if the patient's AE is Grade 2, and the table does not indicate a change in action, if the provider determines that the patient's Grade 2 AE is severe enough to warrant a change in the patient's clinical care (i.e., for medically significant or intolerable Grade 2 AE despite appropriate (maximal) supportive care), then the provider may make that change, as long as the reason for the change is discussed with the PI, and documented in the medical record.

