### **11.3 Adjuvant treatment phase**

Patients will undergo physical exam at each evaluation during treatment and observation. Patients will undergo PET/CT imaging every 12 weeks during adjuvant treatment and observation. Recurrences will be documented.

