16.12 Adjuvant Phase (Post-surgery)

The primary endpoint is the median recurrence-free (RFS) rate. Recurrence-free survival is defined as the time from surgery to radiographic or histologic evidence of local, regional, or distant recurrence of melanoma or death due to any cause

All patients who began adjuvant treatment will be included in the analysis of RFS. Those without evidence of disease recurrence will be censored at the time of their last disease evaluation. For each regimen, the distribution of recurrence-free survival times [denoted as  $RFS(t)$ ] will be estimated using the Kaplan-Meier method. A 90% confidence interval for  $V(t) = \log [-\log (RFS(t))]$  will be constructed and then the inverse transformation  $\exp[-\exp v(t)]$  will be used to obtain a confidence for  $RFS(t)$ . We will estimate RFS for all patients and separately for BRAF-mutated and BRAF-wild-type patients.

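### Section 13.33 takes recurrence-free patients who stop adjuvant atezolizumab for another medical condition off the imaging schedule but leaves them in the primary RFS analysis, and it overlaps with Section 8.2

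*Combined protocol and SAP*

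**What the plan says.** **Routing after adjuvant treatment stops.** Section 13.33: "Patients who discontinue adjuvant treatment due to disease progression or other medical condition will go to the survival follow-up (event monitoring) period". The same sentence adds that "disease and survival information will be collected every 3 months until disease progression and then every 6 months for a maximum of 5 years". Collection until progression only makes sense if patients without recurrence are included.

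The neighbouring rules go the other way. Section 13.32: "Patients who have not had a disease recurrence but develop intolerable toxicity or are refusing further protocol treatment will go to observation phase". Section 13.34 sends patients who complete 8 cycles to observation. Section 8.2: "If all study medications are discontinued due to adverse events during the adjuvant period, the patient should proceed to observation".

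**What each phase schedules.** Section 11.3: "Patients will undergo PET/CT imaging every 12 weeks during adjuvant treatment and observation". The test schedules in 4.1 and 4.2 mark both examination and imaging under observation, which runs every 3 months for up to 3 years after surgery or until recurrence. The table in 4.3 has a single event-monitoring row (every 3 months until progression, at progression, every 6 months afterwards, death, new primary), with no examination, laboratory or imaging entry.

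**Endpoint.** Section 16.12 makes RFS the primary endpoint of the adjuvant phase: "All patients who began adjuvant treatment will be included in the analysis of RFS". A recurrence needs radiographic or histologic evidence. Patients without recurrence are censored at their last disease evaluation.

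**The concern.** A patient free of melanoma who stops atezolizumab because of an unrelated illness is still at risk of recurrence and still in the RFS set. Section 13.33 handles that patient like one who has already progressed. The protocol then no longer requires the scans that would supply the radiographic evidence an RFS event needs, while otherwise similar patients who stop for toxicity or refusal keep them.

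Ascertainment of a primary endpoint therefore varies with the reason recorded for stopping. A recurrence in this group may be dated late, missed, or lost because the patient is censored at the last scan before leaving. Late dating and non-detection both push estimated RFS upward.

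The boundary is also unclear. Section 10.0 defines an adverse event whether or not it is thought to be drug related, and Section 10.81 says the same of attribution. Atezolizumab is the only study drug in the adjuvant phase, so an illness that ends it is arguably an adverse event that has stopped all study medication (8.2: observation) and also another medical condition (13.33: event monitoring). Two sites could follow the same patient on different schedules, each in line with the protocol.

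**Working it through.** The plan gives no figure to reproduce; the check is a comparison of the sections, followed by an illustration of size.

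**1. Follow-up of recurrence-free patients who began adjuvant treatment**

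| Reason for stopping | Section | Phase entered | Scheduled examination and imaging |
|---|---|---|---|
| Completed 8 cycles | 13.34 | Observation | Yes |
| Intolerable toxicity or refusal | 13.32 | Observation | Yes |
| Adverse event stopping all study drugs | 8.2 | Observation | Yes |
| Another medical condition | 13.33 | Event monitoring | No; status every 3 months |

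Scheduled imaging is otherwise consistent. Scans after adjuvant cycles 4 and 8 fall at 4 × 21 days = 12 weeks and 8 × 21 days = 24 weeks, which agrees with 11.3.

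**2. Weight of one patient.** Arm C has 32 patients starting neoadjuvant treatment (16.1112), so at most 32 start adjuvant treatment. One patient is at least 1/32 = 3.1% of the RFS set; four would be at least 4/32 = 12.5%. The number actually affected is not given.

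**3. Illustration of the shift in 24-month RFS.** All inputs here are assumptions: exponential RFS with true 24-month value S = 50% or 70% (monthly hazard −ln S / 24), scans every 3 months, 3% to 20% of patients leaving between 1.5 and 7 months after surgery, leaving unrelated to risk, and 200,000 simulated patients. Kaplan-Meier estimates (%):

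| True RFS | Share leaving | Full schedule | Detected 3 months late | Detected 6 months late | Censored at last scan | Never detected, carried as event-free |
|---|---|---|---|---|---|---|
| 50 | 3% | 49.8 | 49.9 | 50.1 | 49.7 | 51.0 |
| 50 | 12.5% | 49.8 | 50.4 | 51.0 | 49.5 | 54.7 |
| 50 | 20% | 49.8 | 50.7 | 51.7 | 49.4 | 57.6 |
| 70 | 3% | 69.9 | 70.0 | 70.0 | 69.8 | 70.6 |
| 70 | 12.5% | 69.9 | 70.3 | 70.7 | 69.7 | 72.9 |
| 70 | 20% | 69.9 | 70.5 | 71.2 | 69.5 | 74.6 |

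- Detection delay of 3 to 6 months: from 49.9 − 49.8 = 0.1 to 51.7 − 49.8 = 1.9 points upward.
- Never detected and carried as event-free: from 70.6 − 69.9 = 0.7 to 57.6 − 49.8 = 7.8 points upward.
- Censored at the last scan: 0.1 to 0.4 points, slightly downward.

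Which of the last two columns applies depends on whether a status contact in event monitoring counts as a disease evaluation. Section 16.12 does not say.

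**4. Comparison with sampling error.** A simple 90% half-width at n = 32 is 1.645 × √(S(1 − S)/32). This is 14.5 points at S = 50% and 13.3 points at S = 70%. The planned log-log interval will differ somewhat, but the scale is clear.

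**The case against.** **Follow-up for recurrence does not stop.** A reader might infer from 13.33 that it does. The sentence itself requires disease status every 3 months until progression, the same interval as observation, for up to 5 years after registration. Section 18.5 requires supporting documents when a recurrence is found, and deaths remain captured. This stands: what is lost is scheduled examination and imaging.

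**The scans may happen anyway.** Arm C imaging is listed as per clinical standards (4.2), and nothing in 13.33 forbids it. The Case Report Form packet cited in 18.2 is not available and might add detail. This also stands. It means that ascertainment rests on local practice, not that it fails.

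**The observation footnote and 11.3 are not strictly contradicted.** A reader might infer that they are. The footnote sets the length of observation and limits it to operated patients; it does not say that every operated patient enters. Section 11.3 covers only adjuvant treatment and observation. Sections 13.17 and 13.2 also send some non-progressed patients to survival follow-up, but those patients never began adjuvant treatment and so are outside the RFS set. The conflict that does hold is between 8.2 and 13.33.

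**The group is small.** Toxicity, refusal and adverse events are already routed to observation, and adjuvant treatment lasts at most 8 three-week cycles. This stands.

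**The bias is easily overstated.** It is tempting to say that each missed recurrence moves RFS by a full 1/32, or 3.1 points. That treats the patient as event-free, whereas 16.12 censors at the last disease evaluation. If one patient who would have recurred is censored early, the estimate becomes about S × 32/31: 51.6% for 50% (1.6 points) or 72.3% for 70% (2.3 points). Even this supposes that the patient certainly recurs and is never detected. Nor do the documents show that censoring is informative; that would need a link between the intercurrent illness and melanoma recurrence.

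**Conclusion.** The point holds as an unevenness in how a primary endpoint is ascertained, together with an unreconciled overlap between 8.2 and 13.33. The text supports that recurrence-free patients in the RFS set leave the scheduled examination and imaging for one category of reason while comparable patients keep them. It does not support saying that recurrence follow-up ends, that non-informative censoring fails, or that RFS is biased by a known amount.

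Under the assumptions above (3% to 20% leaving, true 24-month RFS 50% or 70%), the likely effect is an upward shift of about 0.1 to 1.9 points from late detection. It could reach about 8 points in the extreme case where recurrences are never detected and patients are carried as event-free. Censoring unrelated to risk moves the estimate by less than 0.5 point; censoring related to prognosis could do more. These shifts are below the sampling error of an estimation-only arm of 32, so no conclusion of the pilot turns on them. The case for amending is that the unevenness is avoidable at almost no cost.

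**What to change.** Reword 13.33 so that only patients with documented recurrence or progression move to event monitoring. Let recurrence-free patients who stop adjuvant treatment for any other reason, including another medical condition, enter the existing observation schedule until recurrence, 3 years after surgery, or refusal. This agrees with 13.32 and 8.2, removes the overlap for intercurrent illness, and changes no dose, treatment or stopping rule.

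The cost is one sentence in an amendment and, for a few patients, surveillance visits already scheduled for everyone else. Patients unable or unwilling to attend can still leave by refusal under 13.4. The change does not remove the similar loss that 13.4 itself creates for patients who leave observation by refusal or by starting non-protocol anti-cancer therapy.

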### 13.4 Observation Phase

Patients who discontinue observation phase due to refusal, disease progression, or initiation of a non-protocol anti-cancer therapy will go to the survival follow-up (event monitoring) period where disease and survival information will be collected every 3 months until disease progression and then every 6 months for a maximum of 5 years post registration.

### 13.5 Ineligible

A patient is deemed *ineligible* if after registration, it is determined that at the time of registration, the patient did not satisfy each and every eligibility criteria for study entry. Protocol treatment is to be discontinued. No further follow-up is required. Subsequent treatment is at the discretion of the patient's medical team.

- If the patient received treatment, all data up until the point of confirmation of ineligibility must be submitted.
- If the patient never received treatment, on-study material must be submitted.

### 13.6 Cancel

A patient is deemed a *cancel* if he/she is removed from the study for any reason before any study treatment is given. On-study material and the End of Active Treatment/Cancel Notification Form must be submitted. No further data submission is necessary.

## 14.0 Body Fluid Biospecimens

### 14.1 Summary Table of Research Blood and Body Fluid Specimens to be Collected for this Protocol

Correlative Study (Section 14.4 for more information)	Mandatory or Optional	Blood or Body Fluid being Collected	Type of Collection Tube (color of tube top)	Volume to collect per tube (# of tubes to be collected)	After registration and prior to start of treatment	After each cycle of neoadj treatment	At end of all neoadj treatment	At time of surgery	≤7 days prior to start of adjuvant treatment	At end of the 4 th and 8 th Cycles of Adjuvant Tx and every 3 months during observation and at disease progression	Process at site? (Yes or No)	Temperature Conditions for Shipping /Storage
Bim, T cell receptor sequencing, mass cytometry, and sPD-L1 studies	Mandatory	Plasma, Peripheral blood mono- nuclear cells (PBMCs)	Sodium Heparin (Green)	10 mL (5)	X	X	X		X	X	No	Ambient for initial transport/ ≤-65°C for storage
cfDNA mutation testing	Mandatory	Blood	Foundation ACT tubes	10 mL (2)	X		X		X		No	Ambient for initial transport
Microbiome	Mandatory	Stool	Stool collection kit	N/A	X		X			X 	No	Frozen
	Mandatory	Buccal (cheek) swab	Swab collection kit	2 swabs	X		X				No	Frozen
	Mandatory	Skin swab	Swab collection kit	30 strokes	X		X	X 			No	Frozen
RNA-Seq†	Mandatory	Frozen tissue	N/A	N/A				X			No	Frozen

†NOTE: RNA-Seq is described in Section 17.3 with other tissue (it is included here because frozen tissue is collected/shipped through BAP)

 Microbiome stool collection ≤2 weeks after last dose of study drug and at time of disease progression

 Skin swab only is collected during surgery

## 14.2 Collection and Processing

### 14.21 Blood

Blood samples will be collected at the clinical phlebotomy areas in the Mayo Clinic and University of Minnesota. Peripheral blood must be kept at room temperature until processing.

Sites outside of Mayo Clinic Rochester must ship immediately overnight (on the same day drawn) at ambient temperature per Section 14.3.

All blood samples will be routed to:

[REDACTED]

At Mayo Clinic in Rochester, sodium heparin blood will be processed over Ficoll to separate PBMCs from plasma. Processed PBMCs and plasma will be stored in

[REDACTED]

### 14.22 Microbiome

Kits will be provided.

Follow instructions in each kit.

Ship all items frozen per kit instructions.

Samples will be processed and stored in

[REDACTED]

## 14.3 Shipping and handling

### 14.31 Kits will be provided.

### 14.32 Shipping Specimens (sites outside of Mayo Clinic Rochester, MN only)

Shipping of the specimens will be requested at completion of each stage of enrollment. Please notify the principal investigators [REDACTED] prior to shipping.

14.322 Stool, buccal, and skin specimens will be shipped according to kit instructions.

14.321 Blood specimens from AZ/FL/UofM will be shipped to:

[REDACTED]

### 14.33 Handling Specimens

Microbiome samples will be processed and stored in [REDACTED]

Blood samples will be transferred to [REDACTED] for processing and storage.

#### 14.4 Background and methodology

##### 14.41 Bim assays

The pro-apoptotic molecule Bim is upregulated in tumor-related T cells upon engagement of PD-1. We have demonstrated that high levels of Bim on pre-treatment tumor-related T cells (reflective of a high level of PD-1 engagement) are associated with clinical responses to anti-PD-1 (Dronca 2016).

Using our previously published flow cytometry technique (Dronca 2016), we will label cells with CD8, CD11b, PD-1, and intracellular Bim. Tumor-related T cells will be defined as CD8+11b+PD-1+. We will determine the frequency of Bim+ tumor-related T cells both prior to treatment and after neoadjuvant therapy, as well as before and after adjuvant therapy. We will correlate baseline and changes in Bim with RFS and pCR.

##### 14.42 Soluble PD-L1 assays

In addition to being expressed as a cell surface ligand in the tumor microenvironment, PD-L1/B7-H1 can be secreted and measured in plasma; soluble PD-L1 (sPD-L1) is associated with prognosis in several tumor types (Frigola 2011). Moreover, in contrast to intratumoral PD-L1, sPD-L1 is associated with a lack of responsiveness to anti-PD-1 therapy in melanoma (Dronca RS et al 2017, and manuscript in preparation).

[figure not shown]
Using our previously published enzyme-linked immunosorbent assay (ELISA) for sPD-L1 (Frigola 2011), we will quantitate sPD-L1 concentrations in patient plasma prior to initiation of neoadjuvant therapy and after neoadjuvant therapy. We will correlate baseline sPD-L1 concentration and the change in PD-L1 concentration from baseline to post-neoadjuvant therapy with response at the time of surgery (pCR versus no pCR) and with RFS.

##### 14.43 Microbiome Studies

Alteration in the gut microbiome has been reported in association with response to immune checkpoint inhibition in both animal models and preliminary reports from human neoadjuvant melanoma trials (Sivan 2015, Wargo 2017). To explore microbiome associations with targeted and immunotherapy response we will collect stool, buccal, skin, and tissue samples before and after treatment. 16S rRNA hypervariable tag sequencing (Jumpstart 2012) will be done to generate microbiome taxa profiles using the DNA samples to partially amplify the microbial (V3-V5 region) 16S rRNA gene through PCR. The PCR product will be purified and quantified before sequencing. Barcoding samples prior to sequencing will yield >20,000 reads/samples, ensuring detection of both dominant (core microbiome) and poorly represented taxa (variable microbiome). We will use quantitatively optimal protocols (Sipos 2010). Reads will be aligned using custom multiple alignment tools (TORNADO v2.0) that merge paired end reads into a single multiple alignment and obtains taxa calls for correlation analysis and utilizing bioinformatic pipelines such as QIIME (Jeraldo 2014, Caporaso, Kuczynski 2012, Caporaso, Lauber 2012). We will assess the proportion of samples with a given organism present (at abundance >0.1%) and report relative abundance and diversity indices in association with treatment response and other variables of interest.

[figure not shown]
#### 14.44 Cell-free DNA (cfDNA)

To assess for changes in circulating tumor DNA, blood samples from patients will be sent to Foundation Medicine for FoundationACT testing. Briefly, multiple commonly mutated genes will be assessed qualitatively and quantitatively in patient cfDNA via multigene sequencing.

#### 14.45 T cell receptor sequencing

T cells undergo somatic gene rearrangement of the T cell receptor Valpha and Vbeta regions during differentiation. In this way, each T cell clone has a uniquely rearranged T cell receptor; this allows different T cells to recognize distinct antigens. By performing sequencing of individual T cell receptor Valpha and/or Vbeta regions, the diversity of T cell clones in a given tissue, as well as the degree of clonal expansion of individual clones, can be determined. To assess for the diversity and clonality of T cell receptors in peripheral blood, processed PBMCs (at least  $5 \times 10^5$ ) will be sent to Adaptive Biotechnologies for T cell receptor sequencing.

In addition, by stimulating PBMCs with candidate neoantigen peptides, we can identify TCR sequences from neoantigen-specific T cells and track the neoantigen-specific T cells at each time point in both blood and tissue. First, somatic mutations will be identified by comparing whole exome sequencing of tumor with whole genome sequencing of blood. Patient HLA class I and class II alleles will be identified from sequencing results as well. Peptides spanning each somatic mutation will be assessed in silico for predicted binding to patient-specific HLA alleles. Peptides that a) contain at least one somatic mutation, and b) are predicted to bind to one of the patient's HLA alleles will be considered candidate neoantigens. Candidate neoantigen peptides will be used to stimulate PBMCs, and TCR sequences from peptide-activated PBMCs will be considered neoantigen-specific TCRs.

